6.5.2 Description of the Visits

6.5.2.1 Inclusion visit

Patients will be documented according to the following procedure: demographics (year of birth, gender, disease and disease duration, results of Chest X-ray and a highly specific interferon- γ -release assay [IGRA] or PPD-test for Tb-screening and RA, PsA, AS, PsO, CD or UC treatment in the past), ESR, CRP; Beliefs about Medicines Questionnaire (BMQ), concomitant treatment other medication or supplement, start of Adalimumab application will be documented in the appropriate eCRF.

6.5.2.2 Follow-up visits

The total treatment period is max. 12 months for each patient.

Approximately 4 follow-up visits are expected over the 12 months period. These visits should occur at an interval of 3 months - "V2", "V3", "V4", "V5".

The visit schedule is to be decided by the investigator according to the routine clinical practice. Intercurrent visits will be documented using the CRF module with the next following visit

number, Visits V2,V3,V4,V5.

Follow up visits shall comprise the following:

V2: ESR,CRP, MMAS, TSQM, RADAI, BASDAI, PASI, HBI, PMS concomitant treatment, Adalimumab-application

- V3: ESR,CRP, MMAS, TSQM, RADAI, BASDAI, PASI, HBI, PMS concomitant treatment, Adalimumab application
- V4: ESR,CRP, MMAS, TSQM, RADAI, BASDAI, PASI, HBI, PMS concomitant treatment, Adalimumab application
- **V5:** ESR,CRP, BMQ, MMAS, TSQM, RADAI, BASDAI, PASI, HBI, PMS concomitant treatment, Adalimumab-application, final statement

Evaluation of the tolerability of the Adalimumab treatment

Any serious adverse events (**SAEs**) of the Adalimumab regimen will be collected throughout this study and 70-days following the last dose of Adalimumab.

Evaluation of the durability of the Adalimumab treatment

Any changes to RA, PsA, AS, PsO, CD or UC treatment and the type of change (dose modification or discontinuation) will be recorded in the data report form, whether the modifications relate to the use of Adalimumab or to the use of concomitant RA, PsA, AS, PsO, CD or UC treatments. If Adalimumab is temporarily interrupted or permanently discontinued before the end of the planned observational period of 12 months, the reason for interruption/discontinuation and the details on the subsequent RA, PsA, AS, PsO, CD or UC treatment, if applicable, will be recorded.

The next routine follow-up visit will be the post interruption/discontinuation visit (see 6.5.1.3).

6.5.2.3 Follow-up visit after temporary interruption or early permanent discontinuation of the Adalimumab treatment (Post interruption / discontinuation visit)

Follow-up visits after temporary interruption or early permanent discontinuation shall comprise the following:

ESR,CRP, Beliefs about Medicines Questionnaire (BMQ), Morisky Medication Adherence Scale (MMAS), Treatment Satisfaction Questionnaire for Medication (TSQM), concomitant treatment, Adalimumab application, final statement.

Evaluation of the tolerability since the interruption/discontinuation of the Adalimumab treatment

All serious adverse events (SAEs) will be reported to AbbVie until 70 days following intake of the last dose of physician-prescribed Adalimumab treatment.

If the physician decides to permanently discontinue Adalimumab this visit will be the termination visit for the patient in the post-marketing observational study.

6.6 **Product Supply**

Since this is a post-marketing observational study, Adalimumabis not supplied by AbbVie. All treatments must be prescribed in accordance with the authorization and local reimbursement guidelines.

Confidential Information

Study treatment:

All regimens will be prescribed according to international and national guidelines for treating RA, PsA, AS, PsO, CD or UC. Adalimumab will be prescribed according to the standard dosing regimen as detailed in the released SPC.

Permitted treatments:

In the context of an observational non-interventional study, the physician is free to initiate any co-prescriptions according to his or her own judgment, although he or she will pay attention to treatments interacting with Adalimumab.

Prohibited treatments:

In the context of an observational study the physician may prescribe according to his or her own judgment although he or she is reminded that Adalimumab must be associated with neither IL-1-antagonists (Anakinra) nor abatacept.

7.0 Management and Reporting of Complaints

A Complaint is any written, electronic, or oral communication that alleges deficiencies related to the physical characteristics, identity, quality, purity, potency, durability, reliability, safety, effectiveness, or performance of a product/device after it is released for distribution.

The investigational product in this trial contains both:

- Biologic compound(s) and
- Device component(s) (pre-filled syringe, pen).

Complaints associated with any component of this investigational product must be reported to the Sponsor. For adverse events, please refer to Sections 7.1.1 through 7.1.6. For product complaints, please refer to Section 8.

7.1 Medical Complaints

7.1.1 Adverse event and serious adverse event definition, serious adverse event categories

An "adverse event" (AE) is defined as any untoward medical occurrence in a subject or clinical investigation subject administered a pharmaceutical product and which does not necessarily have a causal relationship with this treatment. An adverse event can therefore be any unfavorable and unintended sign (including an abnormal laboratory finding), symptom, or disease temporally associated with the use of a medicinal (investigational) product, whether or not the event is considered causally related to the use of the product.

Such an event can result from use of the drug as stipulated in the protocol or labeling, as well as from accidental or intentional overdose, drug abuse, or drug withdrawal. Any worsening of a pre-existing condition or illness is considered an adverse event. Laboratory abnormalities and changes in vital signs are considered to be adverse events only if they result in discontinuation from the study, necessitate therapeutic medical intervention, and/or if the investigator considers them to be adverse events.

An elective surgery/procedure scheduled to occur during a study will not be considered an adverse event if the surgery/procedure is being performed for a pre-existing condition and the surgery/procedure has been documented as pre-planned prior to study entry. However, if the pre-existing condition deteriorates unexpectedly during the study (e.g., surgery performed earlier than planned), then the deterioration of the condition for which the elective surgery/procedure is being done, will be considered an adverse event.

A "serious adverse event" (SAE) is an adverse event, which results in death, is life-threatening, requires inpatient hospitalization or prolongation of an existing hospitalization, leads to persistent or significant disability or invalidity, or is a congenital anomaly/birth defect. If an adverse event meets any of the following criteria, it is considered a serious adverse event (SAE) and has to be reported within 24 hours of the site being made aware of the SAE:

Death of Subject An event that results in the death of a subject.

22

Confidential Information No use or disclosure outside AbbVie is permitted without prior written authorization from AbbVie

- Life-Threatening An event that, in the opinion of the investigator, would have resulted in immediate fatality if medical intervention had not been taken. This does not include an event that would have been fatal if it had occurred in a more severe form.
- HospitalizationAn event that results in an admission to the hospital for any
length of time. This does not include an emergency room visit or
admission to an outpatient facility.

Prolongation ofAn event that occurs while the study subject is hospitalized and**Hospitalization**prolongs the subject's hospital stay.

Congenital Anomaly An anomaly detected at or after birth, or any anomaly that results in fetal loss.

Persistent or SignificantAn event that results in a condition that substantially interferesDisability/Invaliditywith the activities of daily living of a study subject. Disability is
not intended to include experiences of relatively minor medical
significance such as headache, nausea, vomiting, diarrhea,
influenza, and accidental trauma (e.g., sprained ankle).

Important Medical Event An important medical reaction that may not be immediately lifethreatening or result in death or hospitalization, but based on **Requiring Medical or Surgical Intervention to** medical judgment may jeopardize the subject and may require medical or surgical intervention to prevent any of the outcomes **Prevent Serious Outcome** listed above death of subject, life-threatening, (i.e., hospitalization, prolongation of hospitalization, congenital anomaly, or persistent or significant disability/invalidity). Examples of such reaction include allergic bronchospasm requiring intensive treatment in an emergency room or at home, blood dyscrasias or convulsions that do not result in inpatient hospitalization, or the development of drug dependency or drug abuse.

Spontaneous Abortion Miscarriage experienced by study subject.

Elective Abortion Elective abortion performed on study subject.

7.1.2 Severity

The physician will use the following definitions to rate the severity of any adverse reaction being collected as an endpoint/datapoint in the study and for all serious adverse reactions:

Mild	The adverse event is transient and easily tolerated by the subject.
Moderate	The adverse event causes the subject discomfort and interrupts the
	subject's usual activities.
Severe	The adverse event causes considerable interference with the subject's
	usual activities and may be incapacitating or life-threatening.

7.1.3 Relationship to Pharmaceutical Product

This is any report of an adverse event or the absence of an effect or the contamination of an AbbVie product, which may jeopardize the patient, as well as frequently observed inappropriate use or serious abuse. A SAE, that occurs after the therapy has been terminated, has to be reported if it occurs within 5 half-lives of the AbbVie product.

An SAE must meet the following criteria for consideration:

- An identifiable patient
- An e suspected product
- An AE, in utero exposure to AbbVie pharmaceutical or fatal outcome
- An identifiable reporter

The physician will use the following definitions for all serious adverse events, to assess the relationship of the serious adverse event to the use of the pharmaceutical product:

abbvie

	An adverse event is due to an underlying or concurrent illness or effect				
Not Related	of another drug and is not related to the study drug (e.g., has no				
	temporal relationship to study drug or has a much more likely				
	alternative etiology). This is per definition not a serious adverse				
	reaction.				
Probably Not Related	An adverse event has little or no temporal relationship to the study drug				
	and/or a more likely alternative etiology exists.				
Possibly Related	An adverse event has a strong temporal relationship to the study drug				
	and an alternative etiology is equally or less likely compared to the				
	potential relationship to study drug.				
Probably Related	An adverse event has a strong temporal relationship to study drug or				
	recurs on re-challenge and another etiology is unlikely or significantly				
	less likely.				
Definitely Related	An adverse event has a strong temporal relationship to study drug, is				
	known AR, another etiology is unlikely, it disappears respectively				
	reappears with dechallenge respectively rechallenge.				

If an investigator's opinion of possibly, probably not, or not related to pharmaceutical product is given, an alternate etiology must be provided by the investigator for the serious adverse event.

7.1.4 Spontaneously Serious Adverse Event - collection period

All serious adverse events (SAEs) related or not related to Adalimumab will be reported to AbbVie from the time the physician obtains the patient's authorization to use and disclose information (or the patient's informed consent) until 70 days following the intake of the last dose of physician-prescribed treatment.

7.1.5 Spontaneously reported Serious Adverse Event - reporting

In the event of a serious adverse event (SAE), and additionally, any non-serious event of malignancy in patients 30 years of age and younger, related or not related to Adalimumab, the

physician will notify the AbbVie contact person identified below within 24 hours of the physician becoming aware of the even. The physician has to complete the SAE section of the electronic Data Report Form (eCRF). The designated AbbVie pharmacovigilance contact person identified below, will be automatically informed via e-mail in case a SAE occurred, including an attachment containing the entire SAE-form. The local project manager will - in case a SAE occurred - receive this e-mail including the SAE -form for his / her information only.

Aggregate safety data will be integrated into the final study report as well as into periodic safety update reports for the marketed product. Local AbbVie pharmacovigilance contact persons are:

7.1.6 Pregnancy Reporting

Pregnancies in patients will be collected from the date of the first dose through 150 days following the last dose of adalimumab taken during the study. In the event of pregnancy, the physician will notify the AbbVie contact person identified in Section 7.1.5 within 24 hours of the physician becoming aware of the pregnancy.

Information regarding a pregnancy occurrence in a study subject and the outcome of the pregnancy will be collected.

Pregnancy in a study subject is not considered an adverse event. However the medical outcome of an elective or spontaneous abortion, stillbirth or congenital anomaly is considered a **serious adverse event** and must be reported to AbbVie within 24 hours of the site becoming aware of the event!

8.0 Product Complaint

8.1 Definition

A Product Complaint is any Complaint (see Section 0 for the definition) related to the biologic or drug component of the product or to the medical device component(s).

For a product this may include, but is not limited to, damaged/broken product or packaging, product appearance whose color/markings do not match the labeling, labeling discrepancies/inadequacies in the labeling/instructions (example: printing illegible), missing components/product, device not working properly, or packaging issues.

For medical devices, a product complaint also includes all deaths of a patient using the device, any illness, injury, or adverse event in the proximity of the device, an adverse event that could be a result of using the device, any event needing medical or surgical intervention including hospitalization while using the device and use errors.

Any information available to help in the determination of causality by the device to the events outlined directly above should be captured.

8.2 Reporting

The relevant AbbVie Product Complaint contact details are specified below:

In the event of a product complaint related to concerning the investigational product and/or device, the physician has to retrieve the form for product complaints from the InterTrial page (see miscellaneous documents), complete the form and will notify AbbVie, by faxing (fax-no.:

) this form within 24 hours of the physician becoming aware of the event. In instances where a return is requested, every effort should be made by the investigator to return

the product within 30 days. If returns cannot be accommodated within 30 days, the site will need to provide justification and an estimated date of return.

Please return the concerned product to the pharmacy where the patient did purchase it along with the specified description of the complaint. The pharmacy will return it via wholesaler to AbbVie for investigation.

The description of the complaint is important for AbbVie in order to enable AbbVie to investigate and determine if any corrective actions are required.

9.0 Ethics and Quality

All patient data entered in the patient's electronic data report form (eCRF) will be forwarded - without naming the patient - for evaluation to AbbVie. In order to maintain patient confidentiality, instead of date of birth, the patient's age will be documented in the eCRF.

The patients must provide written authorization to the investigator to use and/or disclose personal and/or health data before entry into this PMOS. The investigator will document this authorization in the patient's chart. There are no local law requirements for monitoring, notification /submission of a post-marketing observational study to an ethics committee and/or regulatory body. However, a written confirmation from one of the Lead–ECs will be obtained. In this the following statement should be documented: "According to §2 paragraph 3 of the Austrian Pharmaceutical Act it is an observational study and therefore an evaluation by the ethics committee (EC) is not required". The protocol and the IC/ADU should be provided to the EC for review. It will be submitted to a regulatory body. The study will not be monitored. However in order to assure professional site data-management a qualified Clinical Research Organisation (CRO) as well as a statistician is assigned. Concretely this means that data entered in the eCRFs by the sites will be checked for consistency of data. Inconsistent data will be queried.

10.0 Data Report Forms

Examinations, diagnostic measures, findings and observations routinely performed in patients included in this postmarketing observational study will be entered by the investigator or staff according to the protocol in the data report forms provided by AbbVie. AbbVie Austria will document data in electronic data report forms (eCRF). Completed eCRF visit modules will be sent electronically immediately after completion to the contracted statistician and CRO.

11.0 Data Analysis Plans

11.1 End points

11.1.1 **Primary end point**

Patients' adherence attitudes (beliefs) to maintenance therapy with a scheduled Adalimumab monotherapy or a combination therapy with methotrexate will be assessed at baseline (visit 1 =screening) and at the end of the study at visit 5. Furthermore it shall be investigated whether there are correlations between such beliefs and adherence to maintenance treatment.

11.1.2. Secondary end points

As secondary endpoints the following parameters will be evaluated: changes in the Morisky Medication Adherence Scale (**MMAS**) at visit 2, 3, 4 and 5, changes in the Treatment Satisfaction Questionnaire for Medication (**TSQM**) at visit 2, 3, 4 and 5, changes at the laboratory parameters such as C-reactive protein (**CRP**) and Erythrocyte sedimentation rate (**ESR**).

Changes in the Rheumatoid Arthritis Disease Activity Index (**RADAI**), Bath Ankylosing Activity Index (**BASDAI**), Psoriasis Area and Severity Index (PASI), Harvey-Bradshaw Index (HBI) and the Partial Mayo score (PMS) at visit 2, 3, 4 and 5. The quality of the analyses will depend on the fact that laboratory measurements are not stringent in the context of a non-interventional observational study. Tolerability and safety will be assessed by collection and classification of serious adverse events. Serious adverse reactions observed on treatment with Adalimumab will be described. The duration on treatment with Adalimumab until development

of a serious adverse reaction leading to Adalimumab discontinuation or until escape from treatment will be measured.

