6.4 Study Duration

This PMOS has started In RA, PsA and AS in Feb 2013. The study start for PsO, CD and UC was in November 2014. The estimated end of the patient inclusion is September 2016. Each patient will be observed for a period of max.12 months. Follow-up of patients should enable approximately 5 patient visits (including screening = visit 1) during 12 months. For these reasons, the most likely visits are defined as "V1", "V2", "V3", "V4" and "V5" although numbers

Confidential Information No use or disclosure outside AbbVie is permitted without prior written authorization from AbbVie

and dates will depend only on the decision of the physician. A schedule of activities can be found in the next section. According to the standard of care the approximate frequency of the visits will be 3 months. As a result, failure to meet these suggested dates will not constitute a breach of the protocol.

6.5 Study Conduct and Schedule of Activities:

The study will be conducted in a prospective, single-country, multicenter format. The participating investigator will provide the patient with a prescription for HUMIRA[®]40mg syringe or HUMIRA[®]40mg pen, as the patient can select between two available application devices. Depending on a patient's selection, the investigator will also provide him/her the instructions for appropriate use of the HUMIRA[®]40mg pen (please see Appendix-A) or HUMIRA[®]40mg syringe (please see Appendix-B). Patient safety data and information about co-medications other medications or supplements taken for RA, PsA, AS, PsO, CD or UC will be recorded on electronic data report forms (eCRFs) at study enrollment and during their regularly scheduled visits. If treatment with Adalimumab is interrupted, standard practice is to review the patient after a period of 3 months. If the physician decides to permanently discontinue Adalimumabbefore the end of the planned observational period of 12 months, the reason for discontinuation and the new RA, PsA,AS, PsO, CD or UC treatment regimen prescribed, if applicable, will be documented. The next routine follow-up visit will be the termination visit for this patient in the post-marketing observational study.

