11.2 Plan of Analysis

The statistical analysis shall describe the characteristics of patients included in the survey together with outcomes and clinical tolerability of Adalimumab.

Subject to the level of measurement of the respective variables appropriate descriptive statistics is used: e.g. frequency absolute and/or percental; nonmissing, missing data respectively; mean, standard deviation, where applicable: median, 25th percentile (first quartile) and 75th percentile (third quartile), minimum and maximum, range, calculation of confidence intervals (if applicable). Appropriate graphs are used (e.g. scatterplot, boxplot, histogram, etc.). As the study is an open label non-interventional post marketing observational study there is no working hypothesis allowed!

Compliance with treatments, outcomes and clinical tolerability of treatments will be compared as a function of patient characteristics.

A data analysis plan will be available prior to the conduct of the statistical analysis for the study.

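### Visit-by-visit TSQM and disease-activity changes have no rule for patients who leave after stopping adalimumab, so later-visit means can look better through attrition

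*Combined protocol and SAP*

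**What the plan says.** Section 11.1.2 lists "changes in the Treatment Satisfaction Questionnaire for Medication" at visits 2 to 5, and changes in RADAI, BASDAI, PASI, HBI "and the Partial Mayo score (PMS) at visit 2, 3, 4 and 5". Section 11.2 gives the method as descriptive statistics, for example "frequency absolute and/or percental; nonmissing, missing data respectively; mean, standard deviation". It names no analysis set, missing-data method or longitudinal model, and it defers detail: "A data analysis plan will be available prior to the conduct of the statistical analysis for the study". That later plan is not in the documents.

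On leaving the study, section 6.5 says of a patient who permanently stops before month 12: "The next routine follow-up visit will be the termination visit for this patient in the post-marketing observational study". Section 6.5.2.3 repeats the rule: "If the physician decides to permanently discontinue Adalimumab this visit will be the termination visit for the patient in the post-marketing observational study". Temporary interruption is not stated to end participation.

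The schedule of activities (section 6.5) has a separate early-termination column with no month attached. TSQM and all five indices are marked in it. The list for the discontinuation visit in section 6.5.2.3 includes TSQM but none of the five indices. The TSQM page in Appendix D is headed for visits 3 and 5 and early termination, whereas the schedule, section 6.5.2.2 and section 11.1.2 have TSQM at visits 2 to 5.

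**The concern.** A patient who stops early gives one more assessment at most and then disappears from every later summary. The early-termination form in Appendix D lists lack of efficacy and serious adverse events among the reasons for stopping, and these are tied to the very scores being averaged. If leavers score worse than stayers, the mean moves in the favourable direction from one visit to the next even when no individual changes. A reader of the 12-month figures could not separate improvement from selection. Section 12.0 plans a publication from the final report, so unqualified means would reach readers. The point bears closely on this study because persistence on treatment is part of what it examines.

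**Working it through.** **The plan's own figure.** The only related number is enrolment: 80 + 30 + 30 = 140 and 28 sites x 5 = 140. Both agree. No stopping rate, expected change or SD is stated, so every input below is an assumption shown over a range.

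**Check 1: an outcome-dependent stopping model.** Let z be the standardised score with higher values worse, and let P(stop | z) = 1/(1 + exp(-(a + b z))), with a set so that a share d stops. The shift of the stayers' mean, in SD units towards better, is s = -E[z(1 - P)]/(1 - d). For an index with true mean change -2.0 and SD 2, stayers read -2.0 - 2s. For TSQM with true mean 65 and SD 20, they read 65 + 20s.

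| Stopping d | Log-odds b per SD | s (SD) | Index (true -2.00) | TSQM (true 65) |
|---|---|---|---|---|
| 15% | 0.4 | 0.059 | -2.12 | 66.2 |
| 15% | 0.8 | 0.111 | -2.22 | 67.2 |
| 25% | 0.8 | 0.180 | -2.36 | 68.6 |
| 35% | 0.4 | 0.135 | -2.27 | 67.7 |
| 35% | 0.8 | 0.247 | -2.49 | 69.9 |
| 35% | 1.2 | 0.331 | -2.66 | 71.6 |

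At b = 0 the shift is zero. At b = -0.4 (better patients leave) it is the mirror image: the index reads -2.00 + 0.12 = -1.88 at 15% stopping and -2.00 + 0.27 = -1.73 at 35%.

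**Check 2: no true change at all.** With a share d gone by visit 5 and correlation rho between the tendency to leave and a worse score, the shift is rho x phi(z_d)/(1 - d) SD. At d = 20%, phi(z_d) = 0.280, so rho = 0.3 gives 0.3 x 0.280/0.8 = 0.105 SD and rho = 0.7 gives 0.245 SD. The same range is 0.058-0.136 SD at 10%, 0.149-0.348 SD at 30% and 0.193-0.451 SD at 40%. With rho = -0.3 it is -0.058 SD at 10% and -0.193 SD at 40%. A simulation with N = 140, an assumed intraclass correlation of 0.7 and exits spread over three intervals gave somewhat smaller shifts, 0.09-0.20 SD at 20% and 0.16-0.38 SD at 40%.

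**Check 3: what a mixed model does.** With 33% leaving according to their last observed score and a true change of -2.00, the observed-case mean at visit 5 read -2.30 and the repeated-measures model -2.00. This holds because leaving depended on observed values (missing at random). It does not show that the model removes the bias when leaving depends on unobserved scores.

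**Check 4: counting stoppers as unchanged.** The all-patient mean becomes (1 - d) x stayers' mean. At 35% and b = 0.4 this is 0.65 x -2.27 = -1.48, an error of 0.52 against the truth. The observed-case error in that scenario is 0.27. Such a result is a bound, not a better estimate.

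**Numbers available.** With 20% gone by visit 5, 80 becomes 64 and 30 becomes 24. With 40% gone, 48 and 18. The last group of 30 is shared by CD and UC, so HBI and PMS each rest on fewer still.

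**The case against.** The strongest reply is that the study is descriptive, these are secondary outcomes, and the data analysis plan is still to come. Section 11.2 already reports "frequency absolute and/or percental; nonmissing, missing data respectively", section 11.1.2 measures time on treatment, and Appendix D collects reasons for stopping. All of that is true and useful. It does not say which patients a visit mean describes, and an absent plan cannot be credited with settling that.

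A reader might go further than the documents allow in four ways.

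- That later visits will certainly look better. This needs leavers to score worse. The documents give no stopping rate and no link to response, and the recorded reasons also include loss to follow-up and other causes.
- That the termination value belongs to no scheduled visit. It is taken at the next routine visit, and section 6.5.2.2 files intercurrent visits under the next visit number. With a separate early-termination column in the schedule, the allocation is undefined rather than excluded.
- That visit 5 contains only patients on drug. Someone who stops between visits 4 and 5 has the next routine visit at visit 5, and interrupted patients can also reach it.
- That the sponsor has chosen an observed-case analysis. That is the default reading of a descriptive plan with no missing-data rule, not a stated decision.

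**Conclusion.** The point holds as a risk left uncovered. The documents combine an exit rule tied to stopping the drug, outcomes defined visit by visit, and no rule for termination values or missing visits. Over the assumed range the favourable shift is 0.12 to 0.66 points on an index with a true change of -2.0 (6% to 33%), and 1.2 to 6.6 points on TSQM. These sizes rest on assumed stopping shares, slopes and SDs. The direction rests on leavers scoring worse, which the listed reasons for stopping make plausible but do not establish. The change is worth making because the method is inexpensive and needs no new visits. It does depend on the termination assessments actually being recorded, and on that the documents conflict.

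**What to change.** In the data analysis plan:

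1. State the analysis set and how early-termination values enter the visit summaries.
2. Beside the observed-case means, add for each index and each TSQM scale a repeated-measures mixed model using all visits, with the early-termination value at its actual time. State the missing-at-random assumption. For indices with few patients, such as HBI and PMS, allow a simple covariance structure or pooled reporting.
3. Under each visit mean, print the number still on adalimumab and the number who have left, with reasons.
4. Show a no-improvement-for-stoppers result for the disease-activity indices only, labelled as a conservative bound. TSQM has no visit 1 value, so no improvement is undefined there for anyone without an earlier TSQM score.
5. Reconcile the schedule of activities with section 6.5.2.3 on whether the five indices are recorded at the discontinuation visit. Reconcile the schedule, section 6.5.2.2 and section 11.1.2 with the TSQM page in Appendix D on the TSQM visits. The model can use only what is collected.

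The cost is some extra tables for five indices and four TSQM scales, probably slightly less favourable 12-month figures if leavers score worse, and reliance on missing at random in the added model.
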